Thigh muscle tissue will be obtained as previously described from the left *vastus lateralis* by percutaneous needle biopsy under local anesthesia using aseptic technique and a 6mm University College Hospital needle and a 60cc syringe for suction. Over 700 muscle biopsies have been performed using this technique in older research participants, including HFpEF, with good tissue yields (161±79 mg, >100 mg in 83%) and no serious complications.(164) The portion intended for immunoblot analyses is harvested and immediately stored at -80°C. The portion intended for respirometry will be processed as described below.

Mitochondrial function will be examined comprehensively by analysis of key aspects of mitochondrial physiology (**Table 2**). Measures for this exploratory aim were selected to be relevant to older, obese patients with HFpEF and the effects of RT.

Mitochondrial Physiology	Table 2. Mitochondrial Outcome Assessments
Respiratory Function	
 Respiratory control assessed with complex I, II and β-oxidation specific substrates (isolated mitos) Respirometric kinetics and OXPHOS efficiency (Permeabilized muscle fiber bundles- PmFBs)
Content / Structure / Biogenesis	
 Content - citrate synthase activity; Expression of Porin, cardiolipin, Cox4, and Complexes I-V (Western blot); mitochondrial isolation yields Structure – fiber type, cross-sectional area (histology); Mfn1, Mfn2, MFF, DRP1, Fis1, OPA1 expression (Western blot) Biogenesis - PGC1α, TFAM, SIRT3 expression (Western blot)
Mitochondrial-Mediated Cell Death	
 Bcl-2, Bax, ICE, p53, Fas receptor protein, and Cyclophilin D expression (Western blot) Susceptibility to calcium-induced mPTP opening (PmFBs) Mitochondrial H₂O₂ emitting potential (PmFBs)

Muscle biopsy yield in our preliminary studies in HFpEF averaged 138 mg, sufficient for completion of all proposed experiments; 20-30 mg of tissue to isolate mitochondria,(24) 10-15 mg to prepare permeabilized fiber bundles (PmFB)(6), and the remainder (~100 mg) frozen for protein expression/histochemistry.

Mitochondrial Respiratory Function will be assessed in parallel by complementary techniques using isolated mitochondria and PmFBs.(30; 173; 175) Isolated mitochondria (5 µg) will be assessed with the Seahorse Bioscience XF24 system as a higher throughput system to maximize screening for potential defects/changes in respiratory control at key points in the electron transport chain (ETC) or tricarboxylic acid (TCA) cycle as previously described.(209) Basal (state 2), ADP-stimulated (state 3), non-ADP-stimulated (state 4) and maximally uncoupled (+FCCP) respiration will be determined under substrate conditions that distinguish potential dysfunction at the level of (1) the PDH complex (pyruvate/malate) vs (2) the TCA cycle and/or complex I (glutamate/malate), (3) complex II (succinate/rotenone), (4) complex I + II (glutamate/malate/succinate), and (5) β-oxidation (palmitoyl-carnitine). Data will be expressed as O₂ consumption per mg mitochondrial protein. The PmFB approach will be used to determine in greater detail the kinetics of ADP-stimulated respiration (i.e., Km and Vmax) as previously described.(173; 174) High-resolution respirometry (Oroboros Oygraph-2k, Innsbruck Austria) coupled with direct monitoring of ATP synthesis (fluorometrically) will be used to determine OXPHOS efficiency (ATP /O₂ ratio) during respiration supported by glutamate/malate or succinate/rotenone.(87) All data will be expressed per mg dry weight and normalized for mitochondrial content. RCR, a key pre-planned outcome, will be calculated as the ratio of state 3/state 4.(30)

Mitochondrial Content, Structure, and Biogenesis. Mitochondrial content will be assessed by immunoblot (Porin, cardiolipin, and COXIV) and enzyme activity analysis (citrate synthase).(132) Expression of Complex I-V of the ETC will be determined using the MitoProfile human antibody cocktail (Abcam, ab110411). Regulators of mitochondrial biogenesis (PGC1α, TFAM, and SIRT3) and mitochondrial dynamics (Mfn1, Mfn2, MFF, DRP1, Fis1, and OPA1) will be determined by Western blot.(191)

Mitochondrial Mechanisms for Skeletal Muscle Loss, a phenomenon related to reduced peak VO₂ in HFrEF(3) but never examined in HFpEF, will be assessed by using: 1) expression of Bax, ICE, p53, Fas receptor protein, and cyclophilin D as indices of programmed cell death;(171) 2) Bcl-2 as an index of protection against apoptosis; and 3) calcium retention capacity and H₂O₂ emission in PmFBs as indices of susceptibility to opening of the mitochondrial permeability transition pore and mitochondrial failure.(6; 173)

Physical Activity will be assessed using two accelerometers, the Actigraph GT3X+ and the Lifecorder EX. The Actigraph monitor is a small device worn on the non-dominant wrist, and the Lifecorder monitors is a small device worn on the right hip, attached to the waistband. Both monitors assess variables related to physical activity: energy expenditure, steps, and physical activity duration, intensity, and frequency. Participants will wear both devices for 7 continuous days during baseline and follow-up testing to assess changes in physical activity pre to post intervention. There are no risks associated with wearing an activity monitor.

Study visit timeline.

Table 3. Assessment Timeline	Visit code	SV	BV1	BV2	BV3	Interv.	FV1	FV2	FV3
Activity/assessment	Week number					0-20			
Informed consent, screening, demographics, echocardiogram/Doppler, dietary interview		X							
Physical exam, medical history, medication review		X					X		
RMR, Blood draw, questionnaires, Exercise test			X				X		
SPPB, Muscle strength, DXA & MRI scans				X				X	
Muscle biopsy					X				X
Randomization and dietary education					X				

Analytical Plan

The trial is a 2-arm, randomized, parallel design to test the effect of adding RT to the regimen of CR+AT shown as most beneficial in our recent trial. Peak VO₂ (ml/min) will be the primary outcome measure using an intention-to-treat analysis. Analyses will be conducted using analysis of covariance (ANCOVA) with baseline peak VO₂, age and gender as predefined covariates. Similar analyses will be done for the secondary outcomes, skeletal muscle mass and mitochondrial function, QOL, and other outcomes. Partial correlation analysis adjusting for age and gender will be done to correlate changes in peak VO₂ with the other key outcomes of interest (muscle mass, mitochondrial function, and QOL).

Data Management

The REDCap (Research Electronic Data Capture) system will be used for this trial; as we have used this system previously, many data entry fields, screens, and data checks are in place.

Human Subjects Protection

Informed Consent

Written informed consent will be obtained from each subject. The study coordinator will obtain informed consent in private examination room. Study staff will give adequate time for the participant to review the consent form and ask questions. Each participant will be given a copy of the signed consent form.

Confidentiality and Privacy

Confidentiality will be protected by collecting only information needed to assess study outcomes, minimizing to the fullest extent possible the collection of any information that could directly identify subjects, and maintaining all study information in a secure manner. To help ensure subject privacy and confidentiality, only a unique study identifier will appear on the data collection form. Any collected patient identifying information corresponding to the unique study identifier will be maintained on a separate master log. The master log will be kept secure, with access limited to designated study personnel. Following data collection subject identifying information will be destroyed at the earliest opportunity, consistent with data validation and study design, producing an anonymous analytical data set. Data access will be limited to study staff. Data and records will be kept locked and secured, with any computer data password protected. No reference to any individual participant will appear in reports, presentations, or publications that may arise from the study.

Data and Safety Monitoring

The principal investigator will be responsible for the overall monitoring of the data and safety of study participants. The principal investigator will be assisted by other members of the study staff. If during the study assessments, an incidental medical finding occurs, the principal investigator will be notified immediately. Findings will also be reported to the patient's personal physician for further determination of appropriate care.

Although a DSMB was not required by NIH because it was deemed a low risk protocol, we have elected to utilize a DSMB for this study, the NIH-supported, Pepper Center DSMB, which successfully monitored the recently completed prior cycle of this project, which had a similar patient population, methods, and intervention. This DSMB monitors all Pepper Center supported projects. These DSMB members have appropriate expertise for this project and are: [name] (Chair); [name], [name], [name], [name]. This plan has been approved by [name], Director of the Aging Center and PI of the Wake Forest Pepper Center, and by the NIA program project officer and director.

The DSMB will be charged with monitoring study-wide safety and clinical events on a regular basis (semi-annually). In particular, the DSMB will review the following SAE's and the following specific clinical and safety events: death, hospitalization, hospitalization/ observation unit stay lasting less than 24 hours, emergency room visit, urgent clinic visits, and adverse events occurring while the participant is performing the SECRET II intervention (including angina, syncope/presyncope, palpitations, symptomatic hypoglycemia and/or falls), cardiovascular events (including worsening heart failure, acute coronary syndrome, arrhythmia, and stroke), nursing home placement, and injury (or fall).

Reporting of Unanticipated Problems, Adverse Events or Deviations

Any unanticipated problems, serious and unexpected adverse events, deviations or protocol changes will be promptly reported by the principal investigator or designated member of the research team to the IRB and DSMB.

Long-Term Follow-Up Visit

The purpose of this long-term follow-up visit is to examine the long-term level of weight change (maintenance, continued loss, or regain) following a short-term weight-loss intervention and its effect on exercise capacity, physical function, quality of life, and body composition. A long-term follow-up visit will be conducted to assess changes in weight, VO₂peak, physical function, quality of life, and body composition. All long-term follow-up visits will take place following the completion of the original study. Further, the visit(s) will take place no sooner than 1 year following study intervention completion in any participant. Therefore, this long-term follow-up visit will occur between 8 months and 4 years following study intervention completion for each participant.

The exercise testing, physical performance battery, health-related quality of life, body composition by DXA, and an MRI will be conducted. In addition, physical activity monitoring, basic vital signs (height, weight, blood pressure) will be collected and a review and update of medical history will be performed to check for any possible or new contraindications to exercise testing. The blood and stool sample will also be collected at this visit.

This visit should take ~2-4 hours. It may be done in 1 or 2 visits, depending on study participant desire.

SECRET II Physical Activity Sub-Study (PASS)-COSMED K5

Background

The results of our Studies Examining Caloric Restriction and Exercise Trial (SECRET I) demonstrate that 20 weeks of moderate intensity aerobic exercise (AE) together with caloric restriction (CR) was safe and efficacious for individuals with heart failure and preserved ejection fraction (HFpEF) ¹. Despite many positive changes, the AE + CR combination resulted in a significant reduction of total muscle mass in these HFpEF patients ¹. Therefore, we are currently examining the benefit of incorporating resistance exercise training (RE) to improve body composition and exercise capacity in participants with HFpEF in the SECRET II study.

Moderate intensity AE is generally prescribed at 60-80% of the patient's maximum oxygen consumption (VO_{2peak}) as this level is a safe and effective for HF patients ². Since VO_2 cannot be easily measured during AE or RE, heart rate (HR) is commonly used as a surrogate measure to regulate exercise intensity. While previous research has shown that % HR and % VO_{2peak} during AE are well correlated in clinical populations ³, this relationship has not been examined in HFpEF patients. Performing AE at a low intensity (i.e. < 60% VO_{2peak}) may fail to produce optimal physiological benefits, whereas performing AE at an intensity that is too high (i.e. > 80% VO_{2peak}) may be intolerable and potentially dangerous to these HFpEF patients. Thus, it is important to ensure that HFpEF patients are performing AE and RT in the proper range of their % VO_{2peak} to ensure their safety and to stimulate maximal physiological benefits.

Measuring VO_2 during ambulatory AE or RT was not possible until the development of the portable COSMED K5 system (see photo below). This COSMED K5 system, obtained by the Health and Exercise Science (HES) department in 2016, can be used to measure VO_2 outside of the lab environment, while patients are performing their normal activities, and/or AE and RE. This will be the first time such a measurement/study will be performed in HFpEF patients.

In addition to examining the relationship between % VO_2 and % HR during AE and RE in HFpEF patients, the COSMED K5 allows for the direct determination of energy expenditure (i.e. kcals). In addition to measuring the energy expenditure (in kcals) during AE, we can also determine the additional energy expenditure associated with performing RE in these HFpEF patients. It's unknown if adding RE to AE will result in a significant increase in energy expenditure versus AE alone in HFpEF patients. These findings will have important implications for weight loss and body composition changes and have not been assessed in HFpEF patients.

Based on existing literature and direct experience we developed the following hypotheses;

1. The average % HR will not be significantly different that the average % VO_{2peak} during either the AT only or AT + RT sessions.
2. The average physical activity energy expenditure (PAEE) during a typical exercise session AT or AT + RT will be significantly less than the recommended 300 kcal/day.
3. AT + RT will result in significantly higher PAEE than AT alone.

Methods.

This research project would be conducted in HF patients that are already participating in the SECRET II study funded by the NIH and approved by WFUBMC IRB. Participants in SECRET II are randomly assigned to two groups; CR + AE or CR+AE+RE. The SECRET II intervention is 20 weeks and will eventually enroll up to 90 HF patients over a 4 year period.

This proposed sub-study would be conducted on 15-20 of the HFpEF patients already performing AE with/without RE in SECRET II study. All data collection for this sub-study would take place at the Health and Exercise Science Department's Clinical Research Center under the supervision of [name] and will be stored on encrypted computers and/or in locked files/offices.

Participants in SECRET II would be asked to voluntarily participate in two experimental sessions (one near the beginning and one near the end of their 20 week intervention). For each session the participants would wear the portable COSMED K5 system while performing their normal AE \pm RE exercise session. Expired air will be collected continuously during the entire exercise session that lasts \sim 1 hr. From the expired air collected by the COSMED K5 mask, the VO₂ for each minute will be obtained and compared to HR values that are obtained from a wrist worn heart rate monitor (see photo below). This data would allow us to determine if these HFpEF patients are at the appropriate intensity levels during AE \pm RE.

Furthermore, since we will be able quantify the physical activity energy expenditure (PAEE measured in kcal) from the VO₂ values obtained during both AE and AE + RE, we can compare the two groups to determine if there are additional metabolic costs associated with RT. Finally, to determine the reliability of these measures (VO₂, HR, and kcal) we will ask the first 5 participants in the study to perform a second identical experimental session \sim 1 week after the first session.

Risks.

There are no additional risks, beyond those associated with AE and RE, for the volunteers in this sub-study. Volunteering participants will perform their "normal" AE \pm RE session as part of SECRET II while wearing the COSMED K5 mask. This mask comfortably covers the subject's mouth/nose and allows, through a one-way valve system, for normal inhalation of room air and expiration to the analyzer. If at any point the mask becomes uncomfortable to the participant, it will be removed and the experimental session will be terminated. This is the same mask the participant wears during their baseline exercise test so they will already be familiar with it.

References

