Multiple lines of evidence and our preliminary data indicate that resistance training (RT) could be an ideal addition to CR+AT for HFpEF.(184) (1) RT reliably increases muscle mass, quality, strength, and function, significantly more than AT,(37) and specifically during CR.(36; 50; 74; 76; 77; 101; 144; 184; 225) We found that in older non-HF patients undergoing CR, RT reduced loss of lean mass by 47%, and enhanced body composition and physical function(198) - nearly identical to Frimmel et al who found that RT reduced loss of muscle mass by 48%.(74) (2) In HFpEF, RT improves exercise capacity independent of cardiac function and to a similar degree as AT.(177) In older men, RT significantly increased peak VO₂ (+1.9 ml/kg lean/min) and was associated with increased type 1 fiber area, thigh muscle area, capillary density, and citrate synthase (all of which we have found deficient in HFpEF).(76; 77) (3) RT and AT can have additive effects on peak VO₂(20; 49; 144) In HFpEF, the addition of RT to AT doubled the training-related increase in endurance.(20) (4) RT also improves peak VO₂ by mechanisms independent of muscle mass, including muscle mitochondrial function, blood flow, inflammation, and neuromuscular function.(50; 76; 77; 103; 201; 207; 226) Muscle mitochondrial function is a fundamental driver of peak VO₂ and is reduced in older persons and in HFpEF,(50; 76; 77; 104; 201; 207; 226) and is improved by RT in HFpEF.(226) In diabetics, addition of RT to AT improves muscle mitochondrial content, function and oxidative capacity, resulting in increased peak VO₂.(201) Our preliminary data (Sections 3.D.4.) suggest that: a) muscle mitochondrial content is reduced in HFpEF, and b) is related to the increase in peak VO₂ following CR+AT; c) mitochondrial respiratory function is reduced in obese older adults, and d) improves with RT. (5) RT and AT have complementary effects on muscle and cardiovascular function.(52; 92; 95; 101; 103; 144; 157) (6) Regimens adding RT to AT improve compliance.(50; 225) These data provide a strong rationale for the addition of RT to AT during CR.

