However, RT has never been tested with CR in any type of HF. Furthermore, there are few data regarding RT in HFpEF; a pilot study used a small dose of RT in combination with AT,(58) and another small study included just 3 HFpEF patients.(177) Although initial concerns have been largely allayed regarding the potential effect of RT on left ventricular (LV) function in HFpEF,(135) there remains equipoise in HFpEF. RT can significantly increase arterial stiffness

and LV hypertrophy(153; 225) a potential concern in HFpEF patients who often already have increased arterial stiffness and LV hypertrophy.(106; 124; 137; 230) Therefore, it is important to rigorously test the efficacy and safety of adding RT to CR+AT, as we propose here using state-of-the-art methods.

Objectives

The **primary** aim is to conduct a randomized, controlled, single-blinded 20-week intervention trial of RT added to CR+AT in 84 overweight / obese (BMI \geq 28 kg/m²), older (age \geq 60 years) HFpEF patients to test the following primary hypothesis:

- **The addition of resistance training to CR+AT will improve peak VO₂.**

The **secondary** aims of the study are to test the following secondary hypotheses:

- **Resistance training added to CR+AT will improve retention of skeletal muscle mass.**
- **Resistance training added to CR+AT will improve skeletal muscle mitochondrial function.**
- **The improvement in peak VO₂ with RT will be related to improved skeletal muscle mass and mitochondrial function, and accompanied by improved QOL.**

Peak VO₂ (ml/min) will be assessed by expired gas analysis. Skeletal muscle mass will be measured as thigh muscle area by MRI and total lean mass by DXA.(94; 100) Mitochondrial function and indices of cell death will be assessed by respirometry, protein expression analyses, and enzyme activity assays.(23; 24; 209) QOL will be assessed by the KCCQ instrument. Muscle strength and quality, and cardiac and vascular function will also be assessed.

Methods and Measures

Design

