This is a randomized, controlled, single-blind clinical trial. After baseline assessments, 84 patients with HFpEF aged \geq 60 years will be randomly assigned to 1 of 2 groups: CR+AT or CR+AT+RT. Outcomes will be assessed in blinded fashion at baseline and after the 20week intervention. The primary outcome is peak VO₂ (in ml/min) by expired gas analysis during treadmill exercise to exhaustion. The secondary outcome of skeletal muscle mass will be measured by MRI and DXA. The secondary outcome of mitochondrial function will be assessed by respirometry, protein expression analyses, and enzyme activity assays on *vastus lateralis* muscle biopsy samples with RCR as a pre-planned, key outcome. Other measures will include: health-related QOL by the KCCQ instrument, SF-36, EuroQOL, and CES-D. SPPB; lower extremity strength and power by isokinetic dynamometer; muscle quality; 6-min walk distance; thigh composition and LV and arterial function by MRI; and LV diastolic function by echo-Doppler.

Setting

All study tests and procedures will be performed at Wake Forest School of Medicine and Wake Forest University Clinical Research Center. Testing labs include the Cardiac Ultrasound and Stress Testing lab, Clinical Research Unit, Geriatric Research Center, and the Center for Magnetic Resonance Imaging.

Subjects Selection Criteria

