Confidence in our estimates is enhanced because they are based on data from our recently completed factorial trial of CR and AT using the same patient population and primary outcome. The chosen sample size has adequate power for the primary and secondary aims and QOL. The effect of CR+AT on peak VO₂ was 110.8 ml/min (7.6% relative effect) with a square root of the mean square error for the ANCOVA model being 107.5. To have 90% power to detect a relative effect due to RT of 5.6% (absolute difference of 82.0 ml/min) in peak VO₂ at the 0.05 two-sided level of significance, the study requires 38 evaluable participants per group. In our recent trial, the retention rate was excellent (93%), similar to our previously published trials in HFpEF. To allow for up to 11% loss to follow-up, a total of 42 subjects per group (84 total) will be randomized. In our recently completed study, we observed a 7.4 cm² decrease in thigh muscle area measured by MRI in the CR+AT vs. control group. The square root of the mean square error was 5.98 using analysis of covariance. With 76 evaluable subjects we will have 80% power to detect if the decrease in muscle mass is reduced by 53% (e.g. a difference of 3.9 cm²). In our study of older, non-HF participants, RT had an effect of this magnitude on muscle retention during CR.(198). We will confirm muscle retention with DXA measurement of total lean mass. In our recently completed study; we observed a 2.2 kg decrease (3.2% relative effect) (square root mean squared error of 28.47) providing 80% power to detect a 2.8% relative effect of RT. This sample size also allows adequate power for the secondary aim, mitochondrial function. In our pilot study, RT increased respiratory control ratio (RCR) from 2.78 to 7.23 (160% increase; mean square error of 6.372). The sample size provides 80% power to detect a 60% increase in RCR. It also provides 80% power to detect a 10% relative difference in the KCCQ QOL score. The sample size also provides adequate power to detect increases in confirmatory measures of exercise capacity. In our recent study, we observed a 35.4%, 13.8%, and 13.9% increase in the AT+CR vs. control group in exercise time, VO₂ reserve, and six-minute walk distance respectively. The sample size provides 90% power to detect a 10%, 8%, and 6% increase in exercise time, VO₂ reserve, and six-minute walk, respectively. We will also have 80% power to detect partial correlations as low as 0.30 at the 0.05 two-sided level of significance to examine independent relationships with peak VO₂.

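### The DXA lean-mass power statement cannot be reproduced from its printed error term, and its 2.8% detectable effect is 87.5% of the whole loss seen in the earlier trial

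*Combined protocol and SAP*

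**What the plan says.** The Sample Size section opens its power claims broadly: "The chosen sample size has adequate power for the primary and secondary aims and QOL". It sets 38 evaluable participants per group from peak VO₂ and then turns to muscle mass. For MRI it reports a 7.4 cm² "decrease in thigh muscle area measured by MRI in the CR+AT vs. control group", with a root mean squared error of 5.98, and claims 80% power at 76 evaluable for a 53% smaller decrease (3.9 cm²).

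DXA follows: "We will confirm muscle retention with DXA measurement of total lean mass". The earlier trial is said to have shown a 2.2 kg fall, equal to 3.2%, with a "square root mean squared error of 28.47) providing 80% power to detect a 2.8% relative effect of RT". No unit is printed for 28.47, and no comparator is named for the 2.2 kg.

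DXA has a named place in the outcome. Objectives says "Skeletal muscle mass will be measured as thigh muscle area by MRI and total lean mass by DXA", and Design says "The secondary outcome of skeletal muscle mass will be measured by MRI and DXA". Retention of muscle mass is the first secondary hypothesis.

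**The concern.** The lean-mass loss is in kilograms. Read in the same unit, an error of 28.47 is about 41% of the mean lean mass that the loss implies (28.47 / 68.75). That is far too large for a difference of under 2 kg to be detectable with 38 per group. Either the error term or the detectable effect must be wrong or incompletely labelled.

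A second difficulty does not depend on the misprint. The DXA effect is stated as a percentage of lean mass, while the MRI effect is stated as a percentage of the loss prevented. The two look comparable on the page but are not, and the DXA target is much the larger once both are put on the same scale.

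At stake is how the muscle-mass result is read. If DXA is taken to be adequately powered and is meant to confirm MRI, a non-significant DXA result could count against a real effect that DXA had little chance of showing.

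**Working it through.** **Inputs.** All are from Sample Size unless noted.
- Evaluable: 38 per group.
- Alpha: two-sided 0.05, stated for peak VO₂ and assumed here for DXA.
- DXA: loss 2.2 kg = 3.2%; error 28.47; claim of 80% power at 2.8%.
- MRI: loss 7.4 cm²; error 5.98; claim of 80% power at 3.9 cm².

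**Method.** Two-sample comparison with the noncentral t distribution. Standard error of the difference = SD × √(2/38). Noncentrality = difference / standard error, on 74 degrees of freedom. Under this method the difference detectable with 80% power is 0.651 × SD. Removing 3 degrees of freedom for the ANCOVA covariates changes the powers below by less than 0.1 percentage point.

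**Do the neighbouring statements reproduce?** Yes.
- Peak VO₂: 82.0 ml/min, SD 107.5: power 90.7% (90% stated).
- MRI: 3.9 cm², SD 5.98: power 80.1% (80% stated).
- Respiratory control ratio: mean square error 6.372, SD √6.372 = 2.524; detectable 0.651 × 2.524 = 1.64, which is 1.64 / 2.78 = 59% (60% stated).

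**DXA target in kg.** Implied lean mass 2.2 / 0.032 = 68.75 kg. Rounding of the two inputs allows 2.15 / 0.0325 = 66.2 kg to 2.25 / 0.0315 = 71.4 kg. Then 2.8% is 0.028 × 68.75 = 1.925 kg.

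**DXA power for 1.925 kg under each reading of 28.47.**

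| Reading | SD (kg) | Power for 1.925 kg | Difference detectable at 80% power |
|---|---|---|---|
| Root mean squared error, kg | 28.47 | 6.0% | 18.5 kg (27.0%) |
| Mean squared error, kg² | √28.47 = 5.336 | 34.2% | 3.47 kg (5.1%) |
| Decimal or unit slip (e.g. units of 100 g) | 2.847 | 82.9% | 1.85 kg (2.7%) |
| Back-solved so that 2.8% is exact | 2.956 | 80.0% | 1.925 kg (2.8%) |

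The first two rows do not give the stated 80%. The third comes close: over the rounding range for lean mass its detectable effect runs from 2.6% to 2.8%. The fourth row is a check only. It assumes the 2.8% and the 80%, so it cannot show that either is right.

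**DXA and MRI targets on one scale.** MRI: 3.9 / 7.4 = 53% of the loss. DXA: 2.8 / 3.2 = 87.5% of the loss (1.925 / 2.2 gives the same). With SD 2.847 the detectable 1.854 kg is 84.3% of 2.2 kg.

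**DXA power at the effect used for MRI.** 0.53 × 2.2 = 1.166 kg. Power is 42.2% with SD 2.847 and 39.6% with SD 2.956. If 28.47 is a mean squared error, it is 15.6%.

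**Precision.** The expected 95% confidence interval half-width is 1.9925 × SD × √(2/38): 1.30 kg with SD 2.847 and 1.35 kg with SD 2.956.

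**The case against.** The strongest reply is that this is a labelling slip with no consequence. No unit is printed, so in units of 100 g the error may be correct and only the unit missing. The plan states a detectable difference for DXA and nowhere predicts a particular DXA effect. MRI carries the main power statement for muscle retention, no decision rule turns on DXA significance, and resistance training may add muscle as well as prevent its loss.

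Much of this stands. The missing unit is why the finding is that the statement cannot be reproduced as printed, not that a particular number is wrong. A slip by a factor of ten is also not certain. The same paragraph gives the respiratory control ratio's error as a mean square error, so a mislabelled mean squared error is possible for DXA. In that case the 2.8% would be the faulty figure and the detectable effect about 5.1%. The documents cannot settle which.

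The reply does not remove the difference in scale. Whether training prevents loss or adds muscle, the stated detectable difference between groups is 87.5% of the size of the earlier loss.

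A reader might go further and say that the plan claims adequate DXA power for the 47% smaller lean-mass loss cited in Background, and fails. The documents do not support that. Sample Size makes no DXA claim at 47%, and that figure comes from participants without heart failure. Nor would 47% single out DXA: MRI power at 0.47 × 7.4 = 3.48 cm² is about 71%, also below 80%. A fair comparison uses the 53% that the plan itself adopts for MRI.

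The missing comparator for the 2.2 kg is a small gap. The MRI sentence suggests CR+AT against control, but the DXA sentence should say so.

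**Conclusion.** The concern holds as a reporting error with a modest substantive remainder. As printed, the DXA inputs give about 6% power for a 2.8% effect, or 34% if 28.47 is a mean squared error, against the 80% stated. An error of about 2.85 to 2.96 kg would reconcile the sentence, but its true value is not in the documents.

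If 2.8% is right, DXA reaches 80% power only for a difference 87.5% as large as the whole earlier loss. At the 53% used for MRI, its power is about 40 to 42% with the inferred error. The general claim of adequate power for the secondary aims should therefore not be read as covering DXA at that effect.

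These results assume two-sided 0.05 for DXA, 38 evaluable per group, kilograms for the error, and 68.75 kg as the base of the percentages. The non-reproduction is secure over the rounding range of that base; the diagnosis of a decimal or unit slip is only probable. It would be wrong to infer that the trial is too small: peak VO₂ sets the sample size, and its calculation and the MRI calculation both reproduce.

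**What to change.** In Sample Size:

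1. Check the DXA error term against the earlier trial's output. Print its value, its unit, whether it is a root or a mean squared error, and the comparator for the 2.2 kg.
2. Recompute the difference detectable with 80% power at 38 per group. State it in kg and as a share of the 2.2 kg loss, so that it can be set beside the MRI figure.
3. Describe DXA as supportive of the MRI result, reported with its 95% confidence interval, and exclude it from the general statement of adequate power. With an error of 2.85 to 2.96 kg the expected half-width is 1.30 to 1.35 kg.

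MRI and DXA both remain measures of the muscle-mass outcome, as Objectives and Design have it. The sample size, primary outcome and MRI calculation stay as they are. The cost is one look-up and a few reworded sentences; the DXA statement will probably look less favourable.
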